## **HYPOTHESIS & SPECIFIC AIM**

The combination of Mirtogenol® and bimatoprost will have a superior reduction on intraocular pressure than bimatoprost with a placebo in Hispanic patients with primary open-angle glaucoma. Null hypothesis: The combination of Mirtogenol® and bimatoprost will have no difference on the reduction of intraocular pressure when compared to bimatoprost with a placebo in the Hispanic population with primary open-angle glaucoma (POAG). The specific aim of the study is to determine if the addition of Mirtogenol® to the bimatoprost 0.01% for open-angle glaucoma will have an additive effect on the intraocular pressure in the Hispanic population as compared to bimatoprost plus placebo. The continuous variable of intraocular pressure (IOP) will be compared

using a t-test to determine statistical significance. In addition, the safety of the combination of Mirtogenol® with bimatoprost will be evaluated, but no statistical analysis will be performed.

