## **LITERATURE REVIEW**

Both constituents of Mirtogenol®, Bilberry and Pycnogenol, are powerful antioxidants. The active components of Bilberry (Mirtoselect®) are flavonoid anthocyanosides (anthocyanins). Anthocyanosides are the only flavonoids able to reach the eye as a target organ in experimental animals. Unchanged anthocyanosides demonstrated after oral administration that it is absorbed and distributed into ocular tissues, showing its ability to pass through the blood-aqueous and blood retinal barriers. A meta-analysis of preliminary clinical research shows that taking bilberry anthocyanin 60 mg twice daily for at least 12 months improves visual function in patients with normal tension glaucoma when compared to pretreatment. Anthocyanins are

involved in the stabilization of collagen fibers, promotion of collagen biosynthesis, decrease capillary permeability and fragility.

Pycnogenol® major actions include antioxidant as radical scavenger, anti-inflammatory effects, and stimulation of eNOS synthesis. It has shown to improve pathologic permeability of blood vessels and has been extensively studied for enhancing capillary resistance and integrity in retinopathy. Pycnogenol® has also been found to significantly lower plasma endothelin-1, a vasoconstrictor peptide that affects the trabecular meshwork contractility, which allows for regulatory mechanisms controlling fluid outflow. Pycnogenol® has previously been shown to significantly enhance the generation of endothelial nitric oxide, involved pulsatile choroidal and total choroidal blood flow. Bilberry and Pycnogenol® may interact with immunosuppressant therapy and anticoagulant drugs. Pycnogenol® and bilberry may cause minor side effects that include gastrointestinal discomfort, dizziness, headache and nausea. Serious side-effects have never been reported for Mirtoselect® and Pycnogenol®, despite their long use in ophthalmology, predominantly for diabetic retinopathy.

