Both bimatoprost 0.01% and Mirtogenol® have been shown to have a good tolerability profile and a low incidence of side effects in previous studies. The risks and discomfort that may result because of this study are mild and minimal. Mirtogenol® contains bilberry and Pycnogenol® which may theoretically interact with immunosuppressive therapies and anticoagulant. Mirtogenol® may cause gastrointestinal discomfort, dizziness, headache and nausea. The ophthalmic solution of bimatoprost can cause an increase in the pigmentation of the iris, periorbital tissue (eyelid) and eyelashes, conjunctival hyperemia, conjunctival edema, conjunctival hemorrhage, eye irritation, eye pain, eye itching, eyelid sprain, pruritus eyelids, blurred vision and reduced visual acuity. All visual tests will be noninvasive, but some may cause discomfort and a small chance of cornea abrasion, which usually heals in a few days.

Benefits of the study may include intraocular pressure improvement, visual examinations and tests at no cost and the results of each test performed will be provided at the end of the study. The information in this research study may lead to better treatments in the future for people with glaucoma. Safety measures include non-invasive techniques, standard of care treatment during the duration of the study, ophthalmological evaluations, and assessment tests. Side effects or adverse effects will be reported and evaluated by a specialist and discontinuation of the trial medication will occur if deemed necessary by the treating ophthalmologist. Adverse effects will be documented at each study visit and the treating ophthalmologist will assess possible association of all adverse effects to the trial

medication. A visual acuity score indicating a loss of two or more lines or a cup to disk ratio from mild ( $<0.65$ ) to moderate ( $0.7-0.85$ ) or moderate to severe ( $>0.9$ ) will be considered relevant and a possible discontinuation of the study of participant from the study. Any changes in visual field, central corneal thickness or increase in IOP will be considered relevant and will be evaluated for a possible discontinuation of the participant.

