## VARIABLES

Variable	Type	Description	Measurement
Treatment Groups: (Bimatoprost 0.01% with Mirtogenol ® or Bimatoprost 0.01% with Placebo)	Independent variable (Dichotomus)	Bimatoprost is a prostaglandin inhibitor used to lower IOP. Mirtogenol ® , a potent antioxidant and free radical scavenger supplement, or matching placebo to take daily in addition to bimatoprost.	Mirtogenol ® or Matching Placebo One capsule orally, once daily in the morning

Intraocular pressure	Dependent variable (Quantitative - Continuous)	The fluid pressure inside the eye created by the continual renewal within the eye.	Goldmann Applanation Tonometry
Visual acuity	Dependent variable (ordinal)	Measures the clarity of vision.	Snellen chart
Cup-to-disc ratio	Dependent variable (ordinal)	Measures the progression of glaucoma. Staging glaucomatous damage: Mild: <0.65 Moderate: 0.7-0.85 Severe: >0.9	OCT
Central Corneal Thickness	Dependent variable (Quantitative - Continuous)	Is the thickness of the cornea of the eye.	Pachymetry
Visual field changes	Dependent variable (Dichotomus)	Any type of visual field changes in the participants.	Perimetry
Adverse effects	Dependent variable (Dichotomus)	Adverse effects include: 
 
● Conjunctival hyperemia
 
● Periocular skin pigmentation
 
● Itching
 
● Eye irritation
 
● Foreign body sensation
 
● Growth of lashes
 
● Skin rash
 
● Headache
 
● Nausea
 
● Vomiting
 
● Diarrhea
 
● Dizziness (vertigo)
 
● Hyperglycemic episode
 
● Hypoglycemic episodes
 
	Patients will be questioned on the presence or absence of adverse effects.

		
 
● Bleeding
 
● Other
 
	
--	--	---	--

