## ANALYTIC PLAN

A minimum sample of 72 participants will be used based on the primary efficacy endpoint of intraocular pressure to have an 80% probability to detect a difference between treatments at a two-sided 0.05 significance level. This is based on the assumption that the within-patient standard deviation of the response variable is 3.9 mmHg. Approximately 72 patients will be randomized in a 1:1 ratio to bimatoprost with Mirtogenol® or bimatoprost with placebo (intent-to-treat [ITT] population). There will be 36 patients enrolled in each population. Data will be presented as mean values with standard deviation to describe the population. The 95% confidence intervals assessments will be provided for descriptive purposes. The inferential statistical analysis to be conducted for the primary efficacy endpoint of IOP will be a t-test. All statistical tests will be performed with a significance level set at  $P < 0.05$ . The statistical software to be use will be Minitab. The safety analysis includes presence of adverse effects, changes in visual acuity, visual field, central corneal thickness and cup-to-disk ratio, but no correlation for multiple comparisons will be performed. The intention-to-treat method will be used where all participants who were randomized are included in the data analysis regardless of whether they received their assigned treatment for the entire study. Missing data will not be replaced, instead the last observation or value will be carried forward to account for patients who dropped out and for the statistical analysis.

**Sample Size:** We used the standardized effect size to estimate the sample size needed for the primary efficacy endpoint of IOP. The standardized effect size is the effect size divided by the standardized deviation of the variable. A previous study has reported that the mean on intraocular pressure in treated glaucoma patients is 15.1 mmHg, with a standard deviation of 3.9 mmHg. We would like to be able to detect a difference of 15% or more in the mean intraocular pressure between the two treatment groups. The effect size was calculated to be 0.39 and the standardized effect size is 0.60. Using a two-sided  $\alpha$  of 0.05 and power of 80%, the estimated sample size needed was 36 patients for each group, and 72 patients in total.

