-Headache	 Y  N	 Y  N	 Y  N	 Y  N	 Y  N

-Nausea	[ ]Y [ ]N	[ ]Y [ ]N	[ ]Y [ ]N	[ ]Y [ ]N	[ ]Y [ ]N
-Vomiting	[ ]Y [ ]N	[ ]Y [ ]N	[ ]Y [ ]N	[ ]Y [ ]N	[ ]Y [ ]N
-Diarrhea	[ ]Y [ ]N	[ ]Y [ ]N	[ ]Y [ ]N	[ ]Y [ ]N	[ ]Y [ ]N
-Dizziness (vertigo)	[ ]Y [ ]N	[ ]Y [ ]N	[ ]Y [ ]N	[ ]Y [ ]N	[ ]Y [ ]N
-Hyperglycemic episode	[ ]Y [ ]N	[ ]Y [ ]N	[ ]Y [ ]N	[ ]Y [ ]N	[ ]Y [ ]N
-Hypoglycemic episode	[ ]Y [ ]N	[ ]Y [ ]N	[ ]Y [ ]N	[ ]Y [ ]N	[ ]Y [ ]N
-Bleeding	[ ]Y [ ]N	[ ]Y [ ]N	[ ]Y [ ]N	[ ]Y [ ]N	[ ]Y [ ]N
-Other	_____	_____	_____	_____	_____

Table 3: Code Sheet

Code Sheet	
First and last names	Code number:
1.	
2.	
3.	
4.	
5.	
6.	
7.	

8.	
9.	
10.	
11.	
12.	
13.	
14.	
15.	
16. ...72	

Table 3: Baseline Characteristics

Baseline Characteristics		
Description	Bimatoprost with Mirtogenol ® (n=36)	Bimatoprost with Placebo (n=36)
Age, mean (SD), yrs		
Gender, No. (%)		
IOP, mean (SD), mmHg		
Cup to disk ratio, mean (SD)		
CCT, mean (SD) mm		
Visual acuity, mean (SD)		

Table 4: Primary Efficacy Endpoint

Primary Efficacy Endpoint
---------------------------

Time of Assessment and End Point (Week 12)	Bimatoprost with Mirtogenol® (n=36)	Bimatoprost with Placebo (n=36)	Difference [95% CI]	P-value
IOP				

Table 5: Safety Analysis

Table 3. Safety Analysis		
Variable	Bimatoprost with Mirtogenol® (n=36)	Bimatoprost with Placebo (n=36)
Changes in Vision and progression of glaucoma -no (%)		
Cup to disk ratio		
Central Corneal Thickness		
Visual acuity		
Visual field changes		
Adverse Effects Reported- no. (%)		
Conjunctival hyperemia		
Periocular skin pigmentation		
Itching		
Eye Irritation		
Foreign Body Sensation		
Growth of lashes		
Skin Rash		
Headache		

Nausea		
Vomiting		
Diarrhea		
Dizziness (vertigo)		
Hyperglycemic episode		
Hypoglycemic episode		
Bleeding		
Other		

**Consent form:** Spanish and English (See separate attachment)

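### Gastrointestinal discomfort, one of four effects the protocol expects of the capsule, has no line of its own on the adverse-effect list, the collection form or the safety table (minor)

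*Protocol*

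**What the plan says.** Two sections name the expected effects of the study product. In the LITERATURE REVIEW, Pycnogenol and bilberry "may cause minor side effects that include gastrointestinal discomfort, dizziness, headache and nausea". The risk paragraph under STUDY SUBJECTS says of the combined capsule that it "may cause gastrointestinal discomfort, dizziness, headache and nausea". Both lists have four terms and name gastrointestinal discomfort separately from nausea.

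The adverse-effect row under VARIABLES defines the variable as dichotomous and says how it is obtained: "Patients will be questioned on the presence or absence of adverse effects". It lists 15 named effects and 'Other'. The gastrointestinal entries are "Nausea ● Vomiting ● Diarrhea".

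The Data Collection Form (Appendix Table 2) repeats the list. Each named effect has a Y/N box at baseline and at weeks 4, 8, 12 and 24. 'Other' has a blank line at each visit instead. The Safety Analysis table (Appendix Table 5) has one row per listed effect and a single row for 'Other', with a number and percentage per arm, under the label "Adverse Effects Reported- no".

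Safety is the secondary endpoint (METHODOLOGY AND STUDY DESIGN). HYPOTHESIS & SPECIFIC AIM says the safety of the combination will be evaluated, "but no statistical analysis will be performed". On the denominators, ANALYTIC PLAN says: "There will be 36 patients enrolled in each population".

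**The concern.** Both arms receive bimatoprost, so the capsule's own effects are the ones most likely to differ between arms. A form built to compare tolerability should ask directly about each effect the protocol expects of the capsule. This form asks about three of the four.

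Patients report less when left to volunteer a complaint than when asked about it by name. A write-in line also has no recorded 'No', so a blank may mean that the complaint was absent or that nobody raised it. No safety test is planned, so the table of counts is the whole safety result, and a missing row is a gap in that result. A later analysis plan can recode what was written in, but it cannot recover answers to a question that was never asked.

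**Working it through.** No sample size, power or event figure in the plan bears on this point. The check is a term-by-term match.

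**Step 1: match the four named effects to the three lists.**

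| Effect named in LITERATURE REVIEW and STUDY SUBJECTS | VARIABLES list | Form (Table 2) | Safety table (Table 5) |
|---|---|---|---|
| Gastrointestinal discomfort | none | none | none |
| Dizziness | yes | yes | yes |
| Headache | yes | yes | yes |
| Nausea | yes | yes | yes |

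Three of four have a line and one does not: 1/4 = 25%. The omission is the same in all three places, so it is not a slip in one table.

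**Step 2: see what the existing lines cover.** The list has 16 entries, 15 named and 'Other'. Three of the named ones are gastrointestinal: nausea, vomiting and diarrhea. Nausea cannot stand in for gastrointestinal discomfort, because both source sections name the two side by side. Vomiting and diarrhea may be part of what the broader phrase means. Abdominal pain, bloating and dyspepsia match none of the three, so they can only go under 'Other'.

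**Step 3: what the write-in route does to the counts.** Let p be the true proportion of an arm with residual discomfort and w the share of those cases that get written in. The expected recorded count is 36 × p × w. The protocol gives neither p nor w, so both are assumptions. With p = 15%:

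- w = 1: 36 × 0.15 × 1 = 5.4 patients
- w = 0.5: 36 × 0.15 × 0.5 = 2.7 patients
- w = 0: none

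One patient is 1/36 = 2.8 percentage points of an arm, so losing two or three cases lowers the displayed percentage by roughly 6 to 8 points. If blinding holds, w should be about the same in both arms. The recorded difference between arms is then w times the true difference: it shrinks, but its sign does not change.

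**Step 4: what full recording could show.** If all 5 cases among 72 patients fell in one arm (5/36 against 0/36), the chance of that split in a given arm is (36×35×34×33×32)/(72×71×70×69×68) = 45,239,040/1,678,985,280 = 0.0269. Doubled for either arm, the two-sided Fisher p-value is 0.054. With 36 per arm, even complete capture at this level supports a descriptive count and little more.

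**The case against.** The best defence is that the domain is largely covered and nothing is lost beyond repair. Gastrointestinal discomfort is an umbrella phrase, and nausea, vomiting and diarrhea may be the form's way of spelling it out. 'Other' is open at every visit and kept under the participant's code, so a written-in complaint can be coded and counted by arm. The protocol has adverse effects recorded at each visit, asks the ophthalmologist to judge the association of all of them with the trial medication, and adds a contact one month after the trial medication stops. An interviewer may well ask about other complaints. Table 5 is an empty shell, and the coding of free text is commonly left to an analysis plan.

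Most of this stands, and it rules out several stronger readings:

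- **That the effect cannot be compared between arms at all.** Written-in terms can be counted by arm. The limitation is that the complaint is unprompted and has no row in the table as laid out.
- **That it is the capsule's leading effect.** This rests only on word order. The protocol gives no incidence, and the LITERATURE REVIEW calls these effects minor.
- **That the form is tilted towards bimatoprost effects.** Six of the 15 named lines concern the eye, lids or lashes, counting the unqualified itching line among them. The other nine do not; skin rash is not said to be local.
- **That the trial would wrongly conclude the capsule adds no such effect.** No test or conclusion of that kind is planned for safety.

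The defence does not meet one point. Nothing in the protocol requires anyone to ask about abdominal complaints other than nausea, vomiting and diarrhea, and coding after the fact works only on what was written down.

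**Conclusion.** The omission is real, and its consequence is small. One of four expected product effects is unprompted on the form and has no row in the safety table, while the other three have both. The part at risk is residual discomfort that is not nausea, vomiting or diarrhea. It is likely to be under-recorded relative to the Yes/No items, and Table 5 as drawn would merge it with all other unlisted events.

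This rests on two assumptions: that volunteered reporting is less complete than prompted reporting, and that interviewers keep to the form. How much would be missed cannot be worked out from the protocol; the 15% rate used above is an illustration only. The effect is confined to the descriptive safety comparison. The IOP analysis, its validity and its power are not touched. Severity: minor.

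**What to change.** Before data collection:

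1. Add a line such as *Gastrointestinal/abdominal discomfort* to the adverse-effect list under VARIABLES.
2. Give it its own Y/N box at every visit on the Data Collection Form (Appendix Table 2).
3. Give it its own row in the Safety Analysis table (Appendix Table 5).
4. List 'Other' events by term and arm, in place of one pooled row or beneath it.

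The cost is one more question per visit and one more table row, plus a short listing of write-in terms. No sample size, endpoint or clinical rule changes. For any visit already completed on the present form, only the fourth step can still help, and it recovers only what was written in.

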The study will have five visits: screening and baseline, week 4, week 8, week 12 and week 24 of approximate 30-60 minutes of duration and an addition visit for pickup of the product after the randomization process. An ophthalmological evaluation will be conducted by a glaucoma specialist at each visit. At the baseline visit, the following tests will be performed: visual acuity, visual field evaluation, applanation tonometry, optical coherence tomography (OCT), and pachymetry. At week 4, and week 8 the following tests will be performed: visual acuity and applanation tonometry. At week 12, the following tests will be performed: visual acuity, visual field evaluation and applanation tonometry. At week 24, assessments will include the following: visual acuity, visual field evaluation, applanation tonometry, optical coherence tomography and pachymetry.

The same equipment will be used throughout the study for measurement consistency. Each test will be measured in the morning and the patient will be resting, sitting for at least 10 minutes before measurement. The tests will always be performed by the same person to rule out variations. At each visit, the IOP will be measured twice, with 10-minute intermissions between measurements, and mean values will be recorded. If only one eye is determined eligible as trial eye (meeting the diagnostic criteria for glaucoma), then all assessments will be performed only for the trial eye. If both eyes are eligible, only the eye with highest baseline mean IOP will be included in the statistical analysis. Patients will be instructed not to take any medications within two hours before measurements. Any therapy considered necessary for the patient's welfare will be given at the discretion of the treating physician and will be documented.

Safety measures include non-invasive techniques, standard of care treatment during the duration of the study, ophthalmological evaluations and assessment tests. Side effects or adverse effects will be reported and evaluated by the ophthalmologist at each visit and if deemed necessary the trial medication (Mirtogenol® or matching placebo) will be discontinued and therapy adjusted as

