To ensure confidentiality, all information will be coded so that it cannot be associated with any individual. A separate document (code sheet) will have the participant full name and the code assigned and will be destroyed as soon as data collection has completed. The data collection form will only have the code number to avoid direct connection with the participant's personal information. All data entered into the computerized database will be identifiable by subject code number only. The individuals recruited for this study will be informed of the purpose of the investigation and treatment procedure in accordance with the Declaration of Helsinki and asked to provide written consent for their participation. All participants are required to read and sign detailed consent forms before participating in the study. Participants are advised of the voluntary nature of participation and of their right to withdraw from the project at any time and to require that information about them be removed from data analysis. Each study participant will receive a verbal and written description of the study. Contact information will include name, phone number, address, and email address of the patient and one emergency contact. All information will be kept confidential and protected under the Privacy Rule of the Health Insurance Portability and Accountability Act (HIPAA). The experimental design will be submitted to the Institutional Review Board (IRB) of the Medical Sciences Campus of the School of Medicine of Puerto Rico for approval.

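### Participants who exit after an IOP rise or acuity loss would have that visit's IOP carried forward to week 12; keeping them in scheduled visits is a cheap improvement (minor)

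*Protocol*

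**What the plan says.** The protocol words discontinuation in three ways under STUDY SUBJECTS:

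- **Adverse effects:** "discontinuation of the trial medication will occur if deemed necessary by the treating ophthalmologist". Only the capsule stops.
- **Acuity loss of two or more lines, or a worse cup-to-disk stage:** "a possible discontinuation of the study of participant from the study". This is exit from the study.
- **Visual field change, corneal thickness change or a rise in IOP:** for IOP, an "increase in IOP will be considered relevant and will be evaluated for a possible discontinuation of the participant". No size of rise is given, and the sentence does not say whether the capsule or study participation ends.

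METHODOLOGY AND STUDY DESIGN lets the treating physician give any therapy the patient needs. It schedules tonometry at every visit: "At week 12, the following tests will be performed: visual acuity, visual field evaluation and applanation tonometry". The only follow-up it describes after the capsule stops is a contact one month later. Appendix Table 4 reports the primary endpoint at week 12.

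ANALYTIC PLAN adopts intention to treat, so that "all participants who were randomized are included in the data analysis regardless of whether they received their assigned treatment for the entire study". For missing values, "the last observation or value will be carried forward to account for patients who dropped out".

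The confidentiality paragraph of STUDY SUBJECTS gives participants the right "to require that information about them be removed from data analysis". The sheet linking names to codes "will be destroyed as soon as data collection has completed".

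**The concern.** The trigger for discontinuation is the primary outcome itself. If discontinuation means leaving the study, whether a week-12 IOP exists depends on the IOP readings at weeks 4 and 8. The carry-forward rule then enters the last value, which for an IOP exit is the raised reading that caused it. If the product works, this happens more often on placebo. The week-12 difference can then be overstated, because more high readings are frozen on placebo. It can also be understated, because an active participant who exits early carries a value from before the full effect.

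An acuity exit at week 4 or 8 has the same consequence for the week-12 value, although the carried reading need not be a raised one.

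The data-removal right is a separate and smaller matter. For anyone who uses it, the promise to the participant and the all-randomised rule cannot both be kept.

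**Working it through.** **Which triggers can act before week 12.** The visit schedule and the data collection form put IOP and acuity at weeks 4 and 8. Visual fields are first repeated at week 12, and cup-to-disk ratio and corneal thickness at week 24. On scheduled measurements, only IOP and acuity can therefore remove a participant before the week-12 value; the others bear on week 24.

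**Reference values (ANALYTIC PLAN).** Mean 15.1 mmHg, SD 3.9 mmHg, target 15%, 36 per arm, two-sided 0.05.

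- Target difference: 0.15 × 15.1 = 2.265 mmHg.
- Standardised: 2.265 / 3.9 = 0.581 (the plan states 0.60).
- t-test power at 36 per arm with complete data: 68.1%.

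The plan's 36 per arm is not reproduced at 80% power: an effect of 0.60 needs 45 per arm by a two-sided t-test. That is a separate matter, noted here only because it makes 68%, not 80%, the reference.

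**Simulation of exit plus carry-forward.** The protocol gives no exit rate, correlation or threshold, so these are assumed:

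- normal IOP at baseline and weeks 4, 8 and 12, equal correlation r = 0.4, 0.6 or 0.8;
- a rise from baseline above 0, 2, 3 or 5 mmHg counts;
- the effect is full from week 4, or builds linearly to week 12;
- a rise at week 4 or 8 leads to exit with probability p, and that reading becomes the week-12 value;
- 20,000 trials per setting, two-sided t-test.

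| p | Estimated difference (mmHg) | Shift from 2.265 | Power |
|---|---|---|---|
| 0.10 | 2.184 to 2.315 | -0.08 to +0.05 | 64% to 70% |
| 0.25 | 2.06 to 2.39 | -0.21 to +0.13 | 59% to 72% |

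For example, 2.184 - 2.265 = -0.081 and 2.06 - 2.265 = -0.205. Relative to the target, 0.08 / 2.265 = 3.5% and 0.205 / 2.265 = 9.1%. Type I error was 4.7% to 5.4% throughout.

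Limiting baseline IOP to 21 mmHg, as the inclusion criterion does, changes little: 2.18 to 2.32 mmHg at p = 0.10 and 2.04 to 2.40 at p = 0.25.

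**What drives the range.** At p = 0.25 the low end comes from counting any rise, with an effect that builds linearly. With thresholds of 3 or 5 mmHg the estimate is 2.25 to 2.32 mmHg (p = 0.10) or 2.23 to 2.39 mmHg (p = 0.25). For r = 0.6, a linear effect and p = 0.25, exits are 17% on active and 23% on placebo if any rise counts, about 6 and 8 of 36. At 5 mmHg they are 2% and 4%, about one per arm.

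**Data removal.** Removing one participant who lies 1 SD from the arm mean shifts that mean by 3.9 / 35 = 0.11 mmHg. Removal by name is possible only while the code sheet exists, so it would come before the analysis.

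**The case against.** The strongest reply is that the IOP sentence asks only for a case-by-case safety evaluation. The protocol already allows therapy to be changed within the study, and the analysis includes participants whatever treatment they received. On that reading only the capsule stops, visits go on, and nothing is lost. This is a possible reading, and continued visits are unstated rather than forbidden. It does not settle the matter. The therapy sentence never says that discontinued participants keep attending, the neighbouring sentence on acuity and cup-to-disk ratio says study exit outright, and the contrast with the adverse-effect wording points the same way.

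A second reply is that an exit at week 4 or 8 follows a recorded reading, so missingness depends on observed data and the distortion comes from the carry-forward rule. That is correct. Measuring IOP at week 12 removes the need to carry anything forward for these participants, whichever rule is kept.

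A third reply is that the effect is small and its sign unknown. That stands, and it sets the weight given here.

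On data removal, it is fair to say that the right is an ethical entitlement, arises only on request, and could be handled by reporting. The two sentences still conflict as written.

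A reader might also infer that the one-month contact replaces the remaining visits. The text does not show this; it may be ordinary safety follow-up after the last capsule.

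**Conclusion.** The point holds as a minor one. The wording allows study exit triggered by the primary endpoint, and explicitly by acuity or cup-to-disk change, with a carried-forward week-12 value as the result. The likely shift is about -0.08 to +0.05 mmHg on 2.265 if one rise in ten leads to exit, and -0.21 to +0.13 if one in four does. These figures rest on assumed exit rates, correlations, thresholds and onset of effect, and they model IOP exits only.

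Three stronger readings are not supported:

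- **Every IOP rise ends participation.** The estimate would then range from about 1.5 to 2.7 mmHg, but the protocol says only that discontinuation will be evaluated.
- **False-positive risk is inflated.** Type I error stays near 5% in every setting examined.
- **Data removal biases the comparison in a known direction.** Participants are masked and no removal rate is given, so no direction can be claimed.

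The removal right does contradict the all-randomised rule, but only for those who use it.

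**What to change.** **STUDY SUBJECTS, discontinuation.** State for all the listed triggers (IOP, visual field, corneal thickness, acuity, cup-to-disk ratio) that the ophthalmologist may stop the capsule or adjust therapy, as METHODOLOGY AND STUDY DESIGN already allows. Add that, unless consent is withdrawn, the participant stays in the scheduled visits, has IOP measured at weeks 12 and 24, and is analysed as randomised. Clinical freedom is unchanged.

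**Data removal (lesser).** Subject to IRB approval, state in STUDY SUBJECTS and the consent form that withdrawal ends further collection and that coded data already collected are kept. If removal is retained, state the exception in ANALYTIC PLAN and report the number removed by arm.

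**Cost.** One protocol and consent amendment of a few sentences, with IRB approval. No visits are added, because weeks 12 and 24 are already scheduled. The downside is that some week-12 values will follow a change of therapy, so the comparison includes the effect of that change.
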